5.2 Contact Information

The collection of contact information procedures is the same for all study phases. After screening eligible, participants will be asked if they would like to be contacted by email, phone, or text message for any study communication and will have options to provide contact information for each mechanism. Study staff will not leave messages unless expressly permitted to do so by the participant which also will be documented on this form. If a participant selects the phone option, the study team will ask for explicit permission to leave voice messages that will not include any protected health information or information related to study participation. Participant contact information will be maintained using the same confidential data management practices used for all study data.

5.3 Counselor Training and Intervention Fidelity

We will train counselors in motivational interviewing, CHTC and the relationship building session in a 3-day training session. They will also receive a 3-day training in CTR from the Michigan Department of Health and Human Services. Counselors will demonstrate proficiency via audiotaped role plays prior to being “certified” to deliver sessions. All counseling sessions will be audiotaped (with participant informed consent), and every fourth session will be rated by [name]. Counselors will be provided timely feedback at weekly supervision sessions. For emergent psychosocial problems such as relationship conflict, unemployment, or

loss of residence, a brief problem-solving discussion will be conducted in session and referrals to relevant local agencies and community therapists will be provided, which include a generated list of national services. Counselors will intervene immediately in the event that participants are an imminent threat to themselves or others and will discuss any cases of clinical deterioration with [name] (a Clinical Psychologist) in order to determine whether more intensive treatment is required. In the event there is an immediate situation which requires attention during an assessment or session, [name] will be available. We will use the manualized protocol for rating counselor competence to ensure intervention fidelity. In the RCT (Phase III), counselors will be rated bimonthly as part of supervision. The first 10 session tapes for each counselor will be rated and then subsequently every fourth session will be reviewed by [name]. Counselors identified as having treatment drift will receive booster trainings as necessary.

5.4 Intervention Condition (Phase II and III)

In Phase II, all participant couples will be in the intervention condition in order to pilot the study before the RCT. This dyadic intervention is based on the standard one-session Couples HIV Counseling and Testing (CHTC) session that is now a CDC recommended prevention strategy for male couples and is being tested for adult male couples via video-based counseling. The intervention condition will be modified to include an additional couples sessions, which will be dedicated to relationship skills building. Thus, the intervention will consist of two couples sessions delivered over a two week time period. The first session is the relationship skills session and will focus on defining healthy and unhealthy characteristics of relationships, teaching and practicing effective communication skills, reviewing couples-based sexual health information (i.e., negotiated safety, PrEP, HIV and STI testing), and preparing for engaging in CHTC as a couple.

In Phase III, participants will be randomized after they complete the baseline survey. Participants in the intervention arm will have the option to: (1) participate alone – this involves one CTR + Relationship Skills session within one to two weeks from completing the baseline; (2) participate with their partner – this involves one CHTC + Relationship Skills session; or (3) participate alone in the CTR + Relationship Skills session and also participate with their partner in the CHTC + Relationship Skills session. The choice on how participants want to participate will be recorded in Alchemer, where each option will be explained in detail so that participants can make the best choice for themselves. Regardless of their choice, the participant's initial session should occur within four weeks of enrollment. If they choose to participate with their partner, the invited partner will be screened for eligibility and sent a brief baseline survey before scheduling the CHTC + Relationship Skills session. Participants and their partner (if they choose the couple option) will be mailed an HIV testing kit (OraQuick rapid fluid test) prior to the session. Foundational to this intervention is the individuals or couples talking about and forming a prevention plan using effective communication. Specifically, both sessions are designed to help YMSM learn and practice communication skills and set goals regarding HIV prevention and care which can be used throughout their lives.

In the CHTC + Relationship Skills session, YMSM and their partner will receive all elements of counseling and testing together: pre-test counseling, HIV testing with an OraQuick rapid fluid (saliva) test that will be mailed to participants prior to the session, and discussion of HIV risks, delivery of test results and post-test counseling jointly as a couple. Importantly the dyadic intervention will focus on the future: participants will not be asked to reveal recent risk behaviors/ exposures. Instead the focus is on the couple learning their sero-status together and

building a prevention plan that reflects their relationship goals and sero-status. Foundational to this is the couple talking about and forming a prevention plan together using effective communication skills. Specifically, the session is designed to help YMSM and their partners learn and practice communication skills and set goals regarding HIV prevention and care which can be used throughout their lives.

In the CTR + Relationship Skills session, YMSM will receive all elements of CTR counseling and HIV testing with an OraQuick rapid fluid (saliva) test that will be mailed to participants prior to the session, and discussion of HIV risks, delivery of test results and post-test counseling. Importantly the CTR+ Relationship Skills session will focus on the future: participants will not be asked to reveal recent risk behaviors/ exposures. Instead the focus is on the participant learning their sero-status and building a prevention plan that reflects their relationship goals and sero-status. Foundational to this is the participant talking about and forming a prevention plan and learning effective communication skills to discuss HIV prevention strategies with their partner. Specifically, the session is designed to help YMSM learn and practice communication skills and set goals regarding HIV prevention and care which can be used throughout their lives.

Participants (index partners) randomized to the intervention condition and who choose to do CTR + Relationships Skills will also be given the option to do invite their partner to complete the CHTC + Relationship Skills with them after they complete the individual session. The procedures for the second session will follow those of the CHTC + Relationship Skills session described above.

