Participants will then be mailed STI testing kits. Once they have completed the relationship skills session, they will be mailed HIV testing kits and scheduled for their CHTC session. Surveys will be completed at Baseline and 1-month follow-up. At-home STI testing will be offered at Baseline. With regard to the baseline survey, participants have four weeks to complete the survey from the time the screen eligible. Reminders will be sent to ensure that participants are aware of this study activity. If the baseline is not complete by either of the partners within the four weeks, the couple will be study-stopped. If only one of the participants completes the baseline survey, study staff will continue to follow that participant with the 1-month follow-up survey.

Phase III: If the prospective participant screens eligible, they will enter their contact information into a registration page connected to SMART. After completing the registration page, participants will be instructed to download the SMART app where all subsequent study activities will take place. Participants will be randomized in DFExplore after completing the Baseline survey. Participants randomized to the control arm will complete the study entirely on their own. Those randomized into the intervention arm will have the option to participate alone or with their partner. If they choose to participate with their partner, their partner will be screened for eligibility, consented, and complete a brief survey (not the full baseline survey). The invited partner will not be put into SMART and the only information we will collect is the screener, consent and brief survey data, along with a satisfaction survey after the CHTC session. For invited partners who screen eligible and complete the brief survey, study staff will consent them over the phone prior to the CHTC session. Index participants will complete surveys at Baseline, 3-month, 6-month, and 9-month follow-up. They will be mailed STI kits at Baseline and the 6-month follow-up.

To ensure representation of racial/ethnic minorities, we have a target of 50% in all phases of the study be racial/ethnic minority participants. If enrollment of racial/ethnic minority participants drops below 50%, we will explore additional recruitment strategies

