11.2 Phase III DATA ANALYSIS

We will examine differences between the treatment groups for the index participants using t-tests or Wilcoxon rank sum tests for continuous variables and chi-square tests for categorical variables. We will conduct analyses of our primary HIV and STI testing behavior outcome using regression analyses to compare each active treatment group to the control in pairwise comparison tests at an adjusted significance level of 0.017 to reduce Type-I errors in our 2-arm trial. The proportion of index participants who obtain at least 2 tests at least 3 months apart within the follow-up period will be calculated and presented with corresponding 95% exact binomial confidence intervals. The regression will be run with group assignment only in the model, as well as, controlling for participant characteristics, with a focus on understanding the role of reported relationship dynamics and mechanisms of change (i.e., information, motivation, and behavior) in mediating the outcome. The ability of the intervention to yield increase in PrEP knowledge and efficacy over time will be examined using two separate outcomes. Scores at baseline and all follow-ups will be analyzed using generalized linear models (GLM) with properly-chosen (based on the distribution of dependent variable) link functions to analyze longitudinal PrEP outcome data. The GLMs will be estimated using generalized estimating equations with robust standard error estimates (GEE), which provide an extension of regression analysis to the case of correlated or repeated observations with appropriate modeling of the covariance structure. Models will control for demographic characteristics and study arm and will explore interactions between treatment arm and individual characteristics. The incidence of at-risk sex acts will be calculated as an incidence density, with the numerator being number of individual at risk sex acts, and the denominator being person-years of follow time. Comparisons of the incidence of at-risk sex acts and incidence of STIs will be made by comparing incidence densities across the arms. Period incidence rates (3-monthly incidence density rates) of at-risk sex will be estimated by performing a generalized estimating equations (GEE) Poisson regression analysis of the 3 monthly counts, implemented using SAS PROC GENMOD/ GEE models will control for demographic characteristics, baseline HIV testing history and relationship dynamics and hypothesized mediators, and examine interactions between relationship dynamics and sexual risk-taking. Analysis will also consider differences in changes in information, motivation, and behavioral skills in accordance with the RELO-IMB model.

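### The plan compares unnamed active groups with control at a three-comparison level in a two-arm trial; if the groups are the three self-chosen modes of participation, those comparisons are not randomised.

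*Protocol*

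**What the plan says.** The order of events is set in Protocol 5.1: "Participants will be randomized in DFExplore after completing the Baseline survey". For the control arm: "Participants randomized to the control arm will complete the study entirely on their own". For the intervention arm: "Those randomized into the intervention arm will have the option to participate alone or with their partner".

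Protocol 5.4 gives the options. "Participants in the intervention arm will have the option to: (1) participate alone" opens the list; the other two are a couple session, or both an individual and a couple session. It adds: "The choice on how participants want to participate will be recorded in Alchemer". The mode is not final at that point. Those who start alone may later "invite their partner to complete the CHTC + Relationship Skills with them after they complete the individual session". The couple session also depends on someone else, since "the invited partner will be screened for eligibility and sent a brief baseline survey before scheduling".

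Protocol 5.5 describes a 1:1 allocation to two conditions. The only stratification mentioned is by race and ethnicity (Study Abstract, Recruitment).

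On analysis, Protocol 11.2 and the SAP use the same words: for the HIV and STI testing outcome, regression will "compare each active treatment group to the control in pairwise comparison tests" at an adjusted level of 0.017. The same sentence calls the study a 2-arm trial. Neither text says which active groups are meant, and neither gives an estimand or a method for mode of participation.

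**The concern.** A two-arm trial has one active group and one randomised comparison. The analysis text speaks of several active groups and sets a significance level for several comparisons. The only set of three active groupings that Phase III describes is the three modes, so an analyst could reasonably take the sentence to mean mode versus control.

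Those comparisons would not be protected by randomisation. Men who bring a partner to a joint session have chosen to do so and have a partner who is willing and eligible. They may well differ from the others in communication and relationship quality before any session takes place. Controls are not offered the choice, so no control group is defined by the same choice. A difference between couple-mode participants and all controls would mix the effect of the intervention with these prior differences.

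The temptation is real because the SAP title presents the study as a dyadic approach among couples, and readers will want to know what the couple session adds. Couple uptake is also unknown: Protocol 3.2 reports that no Phase II participant completed a session.

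**Working it through.** **The plan's own figure.** For three comparisons at an overall 0.05, Bonferroni gives 0.05/3 = 0.0167 and Sidak gives 1 - 0.95^(1/3) = 0.01695. Both round to 0.017. Two comparisons would give 0.025 and four would give 0.0125. So 0.017 is a level for three comparisons, while 1:1 allocation to two conditions supplies one.

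**Timing of the choice.** Protocol 5.4 does not date the choice form. Protocol 4.8 and 12.3 both describe the choice of couple participation as made by someone already randomised to the intervention arm. The measures listed in 6.1 and 6.4 contain no question on preferred mode put to everyone at baseline. The nearest is willingness to use prevention strategies, in a list that includes CHTC; that is not a choice of study mode.

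**Size of the bias if modes are compared with control (illustration).** From the documents: 320 participants at 1:1, so 160 per arm. Assumed, because the documents give neither: a share p choosing the couple mode, and an outcome gap d (in SD) between choosers and non-choosers with no intervention effect at all. The outcome is taken as continuous, with no adjustment and no attrition.

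The control mean is the mix of both types, so:

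- bias = (1 - p) × d
- SE = sqrt(1/(160p) + 1/160)
- two-sided rejection rate at 0.017, critical value 2.387

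Example, p = 0.3 and d = 0.3: bias = 0.7 × 0.3 = 0.21; SE = sqrt(1/48 + 1/160) = 0.165; ratio 1.28; rejection rate 13.3%.

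| p (couple n vs 160) | d = 0.2 | d = 0.3 | d = 0.5 |
|---|---|---|---|
| 0.3 (48) | 0.14 SD, 6.3% | 0.21 SD, 13.3% | 0.35 SD, 39.7% |
| 0.5 (80) | 0.10 SD, 5.0% | 0.15 SD, 9.9% | 0.25 SD, 28.7% |
| 0.7 (112) | 0.06 SD, 3.1% | 0.09 SD, 5.0% | 0.15 SD, 12.1% |

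If the gap exists only in a baseline score that correlates 0.5-0.7 with follow-up (also assumed), d = 0.3 shrinks to 0.15-0.21. The rate for p = 0.5 to 0.3 then falls to 3.5-6.8%.

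**What a baseline preference item would support.** Comparing arms among those who state a couple preference has 160p per arm. The detectable difference at 80% power is (1.960 + 0.842) × sqrt(2/n):

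- p = 0.5, 80 vs 80: 0.44 SD
- p = 0.3, 48 vs 48: 0.57 SD
- whole arm, 160 vs 160: 0.31 SD at 0.05, or 0.36 SD at 0.017

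At 80% retention, the low end of the target in 6.4, the first two become 0.50 and 0.64 SD. A difference in arm effect between those who prefer the couple mode and those who do not has SE sqrt(2/(160p) + 2/(160(1 - p))). It would have to be 0.63 SD (p = 0.5) to 0.68 SD (p = 0.3) to be detected, before attrition.

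**The case against.** The strongest reply is that the plan never names a comparison by mode. Objective 2 compares the adapted intervention with CTR alone, 3.2 defines the intervention as one package with either form of session, and 11.2 runs its regression first with group assignment only. Making the partner optional was a deliberate change after Phase II. On this view the reference to several active groups is a leftover, and the defect is one of wording. That may be so. It does not settle the matter, because the text as it stands does not say which groups are compared, and the 0.017 level is out of step with two arms on either reading.

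A second reply is that the error rates above do not describe a planned test. That is right. The 0.017 level is attached to the HIV and STI testing outcome, a proportion, and no test of a scale score at 0.017 is stated. The figures show direction and rough scale only.

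A third is that baseline measures of satisfaction, commitment, closeness, communication and sexual agreements are to be collected before randomisation, so choosers could be matched with similar controls. This stands in part: adjustment can reduce the bias, but only under an assumption of no unmeasured confounding. Using allocation as an instrument for the couple session does not avoid that problem, because participants who take part alone also receive relationship skills, so allocation can affect the outcome without any couple session.

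A reader might infer that the main comparison of the trial is compromised. It is not: all index participants compared by randomised arm keep the full protection of randomisation.

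**Conclusion.** The point holds as an ambiguity with a biased reading, not as a flaw in the randomised comparison. The documents establish that allocation precedes the choice, that the choice is offered in one arm only, and that the analysis text sets a three-comparison level for unnamed active groups in a two-arm trial. If those groups are the modes, the comparisons are self-selected. With 30-50% choosing the couple mode and a 0.3 SD unadjusted gap that persists to follow-up, the bias is 0.15-0.21 SD and the false-positive rate 10-13% against a nominal 1.7%. Both inputs are assumptions, and a fading gap or adjustment lowers the result.

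Two stronger readings are not supported. One is that the plan specifies mode-versus-control tests; no section does. The other is that the trial cannot answer its own question; Objective 2 concerns the offered package, and the whole-arm comparison answers it. What the design cannot isolate from randomised groups is the effect of couple delivery as against individual delivery.

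**What to change.** 1. In Protocol 11.2 and the SAP, replace the reference to several active groups with one comparison of all index participants by randomised arm.
2. Reconcile the 0.017 level with that single comparison. If a reduced level is kept for another reason, such as several outcomes, state the reason. Keeping it moves the whole-arm detectable difference from 0.31 to 0.36 SD in the illustration above.
3. Label any comparison by mode actually taken as descriptive and non-randomised.
4. Add one baseline item for all participants, before randomisation, asking whether they would prefer to take part alone, with a partner, or both. Use it for a pre-specified secondary estimate of the arm effect by stated preference. Describe the result as the effect of the offered package among those who prefer the couple option, not as the effect of couple versus individual delivery.

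The first three changes cost only wording and can be made at any time before analysis. The fourth costs one survey item and cannot be recovered validly once participants know their allocation. Its drawbacks are that stated preference may differ from the later choice, that precision within a preference group is low (0.44-0.57 SD detectable before attrition), and that asking controls about an option they do not receive may cause some disappointment.

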5.5 Registration & Randomization (Phase III RCT)

In Phase III, after completing the baseline survey participants will be randomized via DFexplore in a 1:1 ratio into the intervention or control condition. In order for interventions to be evaluated as potential “best evidence”-based interventions through CDC’s Prevention Synthesis Research activity, data must be available for at least a single follow-up time point for at least 70% of participants. We will use best practices to retain participants (e.g., comprehensive locator information that includes participants' cell phone number, and e-mail), while being sensitive to undue disclosure of YMSM participating in the study. Depending on the participants' preferences provided upon registration, contacts will be made initially with the preferred mode of re-contact (for example, by SMS text message); if still unresponsive, other available modes (e.g., phone call) will be used. The study will use a HIPAA-compliant web-based platform entitled Study Management and Retention Toolkit (SMART), which is a SaaS (Software as a Service) based mobile application aiding studies with various aspects of participant recruitment, study implementation, and retention. SMART is a licensed service of the Center for AIDS Research (CFAR) at Emory University, Prevention Science Core. We will follow YMSM for 9 months and have contact with them every three months. The small time frames between assessments helps us to respond quickly to retention concerns. Incentives for completing the baseline and follow-up surveys will be \$40 per individual, per assessment. If a participant completes all three follow-up surveys, they will receive an additional \$40.

For both conditions, participants will be taken to an online calendar asking them to schedule their first session. The calendar will be populated by study staff per their availability and will reflect local time zones. The page will explain the session format, will provide detailed instructions on using the Zoom video-chat software, and will contain a list of instructions for participating in the sessions (e.g., audio and visual privacy, etc.). For both conditions, the

sessions will be about 45 minutes... Each session will be delivered via Zoom, the HIPAA-compliant video-chat software that can be used on a PC, tablet or smartphone.

